11.1.2 NRS for pain

The 11-point NRS for pain ranging from 0 (no pain) to 10 (worst imaginable pain) will be reported based on the average pain experienced during the 7 days before the study visit. Change from baseline in average NRS values will be calculated for Weeks 1 and 2, Months 1, 2, 3, 6, 9, and 12 as the post-baseline value minus the baseline value. Negative changes from baseline indicate improvement.

For all patients, the NRS (7-Day recall) collected at Visit R1 will serve as the NRS baseline value.

11.1.3 Daily opioid dose

Opioid doses will be recorded for each patient, including both the maintenance dose and dosing for breakthrough pain. However, the daily opioid dose in morphine equivalents (mg/day) will be calculated using only the maintenance dosing information. The mean daily opioid dose (mg/day) for an interval will be calculated as the sum of daily opioid doses

(mg/day) for the interval divided by the number of days within the interval in which the data were collected. The mean daily opioid dose will be calculated for the following time intervals: randomization in this study to Month 1, Months 1 to 3, Months 3 to 6, Months 6 to 9, and Months 9 to 12. For rollover patients, the mean daily opioid dose will also be calculated for the following time intervals: randomization in the previous NKTR-118 study (D3820C00005 or D3820C00007) to Months 1, 3, 6, 9, and 12.

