Adult patients who are receiving a stable maintenance opioid regimen (total daily dose of 30 to 1000 mg of oral morphine, or equianalgesic amount[s] of 1 or more other opioid therapies for a minimum of 4 weeks) for non-cancer-related pain and who report a history of <3 spontaneous bowel movements (SBMs)/week and at least 1 OIC associated symptom at screening and have a confirmed diagnosis of OIC will be eligible to be randomized.

Confirmed OIC is defined as:

- Documented <3 SBMs/week on average over the 2-week OIC confirmation period. Patients with uneven distribution of SBMs across the 2-week OIC confirmation period (0 SBMs in 1 week with ≥ 4 SBMs in the other week) will be excluded. In

addition to the SBM frequency criterion, patients must report ≥ 1 of the following symptoms in at least 25% of the bowel movements (BMs) recorded in the electronic diary (eDiary) during the OIC confirmation period: Bristol Stool Scale (BSS) stool type 1 or 2; moderate, severe or very severe straining, incomplete BM. Patients who have 0 BMs over the 2-week OIC confirmation period will not be randomized.

Investigational product, dosage and mode of administration

NKTR-118 25 mg tablets

Comparator, dosage and mode of administration

The study will include a Usual Care arm. For the Usual Care arm, investigators will be permitted to choose constipation treatment according to their best clinical judgment.

Duration of treatment

The study duration will be 54 to 58 weeks. The study will consist of 52 weeks of open-label treatment followed by a 2 week follow-up period. In addition, new patients will undergo an initial screening period lasting up to 2 weeks, and a 2-week OIC confirmation period, during which the diagnosis of OIC and stability of opioid regimen will be confirmed.

Outcome variable(s):

- **Safety**
 - Incidence, nature, and intensity of adverse events (AEs), treatment-related AEs, serious adverse events (SAEs), AEs leading to discontinuation, and specific safety areas of interest
 - Mean daily prescribed opioid dose
 - Mean bisacodyl dose per week (NKTR-118 group only)
 - Change from baseline in Numeric Rating Scale (NRS) pain score
 - Observed values and change from baseline in composite score of modified Himmelsbach scale
 - Changes in vital signs and physical examination
 - Changes in laboratory assessments (ie, chemistry, hematology, and urinalysis [U/A])
 - Changes in electrocardiograms (ECGs)
- **Health economics**

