NKTR-118 was well-tolerated in the Phase II study at 5 and 25 mg/day with the most commonly reported side effects being GI in nature (abdominal pain, diarrhea, and nausea) and most frequent in the 50 mg cohort. The frequency of any GI AE was 53% in the 25 mg/day dose group and 48% in the corresponding placebo group. In the 50 mg/day dose group, the GI AE frequency was 69% and 27% in the corresponding placebo group. In the 5 mg/day dose group, the frequency was 46% and 34% in the corresponding placebo group. Most of the AEs were rated mild or moderate. During the double-blind phase, a total of 12 patients discontinued the treatment permanently due to AEs (10 patients in the 50 mg dose group, 1 patient in the 25 mg/day dose group, and 1 patient in the 5 mg/day dose group). Most of the discontinuations were due to GI AEs. There was 1 serious adverse event (SAE) of upper abdominal pain in the 50 mg dose cohort, which was considered to be related to the study drug by the investigator. The patient was briefly monitored in a hospital setting due to this event, which resolved spontaneously without medical sequelae. No reversal of analgesia was seen at any dose in Phase II, as measured by changes in the daily opioid dose or by Numerical Rating Scale (NRS) for pain. A significant increase in total Clinical Opioid Withdrawal Scale (COWS) score for the NKTR-118 50 mg group was noted as compared with placebo at Day 1 of the double-blind treatment period. When the GI component of the COWS instrument (eg, diarrhea, abdominal cramps) was removed from calculation of total COWS scores, there was no longer a significant difference, indicating a lack of increase in the components of the scale that reflect CNS withdrawal. Although these data suggest that the risk for reversal of analgesia or precipitation of opioid withdrawal is unlikely, it is recommended that investigators remain vigilant regarding this potential effect of NKTR-118.

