Laxative use is prohibited during the OIC confirmation period (for new patients) and throughout the treatment period for NKTR-118 patients, since these medications could confound the efficacy of NKTR-118. However, patients who do not respond to study treatment with NKTR-118 may take a laxative rescue medication if a BM has not occurred within at least 72 hours. In such cases, bisacodyl has been chosen as a first-line treatment because it is efficacious and suitable for as needed administration. Further guidance is provided on the use of bisacodyl as well as an enema if bisacodyl is ineffective.

Peripheral μ -opioid antagonists are prohibited for use as laxatives in the Usual Care arm because their similarity to NKTR-118 could potentially confound results. In accordance with

the latitude offered to investigators in determining Usual Care treatment, no specific laxative rescue guidelines are provided for the Usual Care arm. To minimize confounding influences, an effort has been made to exclude patients with constipation or diarrhea for reasons other than OIC.

NKTR-118 is expected to improve the symptoms of OIC by blocking the peripheral effects of opioid medication without inducing central opioid withdrawal symptoms or interfering with analgesia. Although there was no indication of opioid withdrawal symptoms or reversal of analgesia in the Phase II study, the current study includes the modified Himmelsbach scale to assess withdrawal symptoms, and the NRS along with ongoing assessment of daily opioid dose to assess pain.

The C-SSRS is included as a safety measure to assess risk for suicidality in this patient population.

Although Phase II data did not show changes in liver enzymes, liver function tests will be monitored after randomization, and specific guidelines for handling possible elevations in liver enzymes are included in the protocol.

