5.6 Concomitant and post-study treatment(s)

5.6.1 Pain medication guidelines

Throughout the study, investigators will be encouraged to maintain a patient's baseline pain control regimen, with dose adjustments made as needed in accordance with the patient's clinical needs. Investigators will retain latitude in making these adjustments as clinically indicated, but it is recommended that the guidelines for the ongoing management of pain in the study reference manual ([Chou et al 2009](#)) serve as a framework for dose adjustments on-study. It is anticipated that the majority of the patients in this study will be receiving a long-acting opioid for control of background pain and an immediate-release opioid PRN for breakthrough pain, although some may be receiving only a short-acting opioid on a scheduled basis.

It is recognized that some patients may have their pain managed by personal physicians who are not connected with the study. In such cases, patients will be asked to notify their personal physicians of their participation in the study, and communication between the patient's personal physician and the investigator is strongly encouraged. Although it is desirable that patients be maintained on a stable opioid regimen during the study, should changes in the maintenance opioid regimen be necessary they should be reported to the site at the next study visit and recorded on the maintenance opioid eCRF. Opioid medication for breakthrough pain should also be reported at the next study visit and recorded on the breakthrough pain medication eCRF.

Concomitant non-opioid analgesics will not be prohibited, but investigators will be encouraged to maintain such drugs at stable doses on-study if possible.

Unless there is a need for urgent intervention, patients will not be allowed to take any additional medication for pain control other than their maintenance opioid regimen and approved opioid medication for breakthrough pain without the prior agreement of the investigator (or their personal physician, if pain is managed outside the study, in which case the investigator must be notified of any changes). This includes over-the-counter treatments for pain.

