6.3.1 Safety variables

Safety variables include:

- Incidence, nature, and intensity of AEs, treatment-related AEs, SAEs, AEs leading to discontinuation, and specific safety areas of interest
- Mean daily opioid dose for Months 1, 3, 6, 9, and 12
- Mean bisacodyl dose per week for Months 1, 3, 6, 9, and 12 (NKTR-118 group only)
- Change from baseline in NRS pain score for Week 1, Week 2, Months 1, 2, 3, 6, 9, and 12.
- Observed values and change from baseline in composite score in modified Himmelsbach scale for the evaluation of centrally mediated opioid withdrawal symptoms for Week 1, Months 1, 3, 6, 9, and 12
- Changes in vital signs and physical examination
- Changes in laboratory assessments (ie, chemistry, hematology, and U/A)
- Changes in ECGs

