6.3.6 Daily opioid dose

Opioid doses will be recorded for each patient and the daily opioid dose in morphine equivalents will be calculated. Opioid breakthrough pain medication will be recorded on the relevant eCRF at Visit S1 for new patients (to cover medication taken during the previous 60 days). Information obtained at Visit S1 will be entered into the eDiary to facilitate eDiary recording. Between Visits S1 and R1 opioid breakthrough pain medication will be captured only in the eDiary. At all visits from Visit R1 on, opioid breakthrough pain medication will be recorded on the relevant eCRF for all patients. The daily maintenance opioid dose will be recorded on the relevant eCRF at all visits for all patients. A home diary will be assigned to each patient to facilitate collection of opioid breakthrough pain medication usage.

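### Daily opioid dose counts maintenance opioid only, and the protocol specifies no analysis of breakthrough use after randomization, so PRN compensation for lost analgesia would not show in it

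*Protocol*

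**What the plan says.** The protocol gives daily opioid dose a purpose. Section 3.2 says the study includes "the NRS along with ongoing assessment of daily opioid dose to assess pain". Section 1.4 reports that Phase II saw no reversal of analgesia "as measured by changes in the daily opioid dose or by Numerical Rating Scale (NRS) for pain", so the same pair of measures was used there.

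The data collected cover the whole opioid intake. Section 11.1.3 begins: "Opioid doses will be recorded for each patient, including both the maintenance dose and dosing for breakthrough pain". Section 6.3.6 adds: "At all visits from Visit R1 on, opioid breakthrough pain medication will be recorded on the relevant eCRF for all patients". A home diary supports this between visits (sections 3.1 and 6.3.6). Section 5.6.1 expects most patients to take a long-acting opioid plus "an immediate-release opioid PRN for breakthrough pain, although some may be receiving only a short-acting opioid on a scheduled basis".

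The derived variable is narrower. Section 11.1.3 continues that "the daily opioid dose in morphine equivalents (mg/day) will be calculated using only the maintenance dosing information". The synopsis lists "Mean daily prescribed opioid dose" and section 6.3.1 lists "Mean daily opioid dose for Months 1, 3, 6, 9, and 12". Section 12.2.1 summarizes the mean daily opioid dose by interval. None of these places, nor any other analysis section, gives a variable or summary for breakthrough use after randomization.

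**The concern.** An opioid antagonist that reached the central nervous system could weaken pain control. A patient who notices this has two routes to more opioid: a higher maintenance dose, or more PRN doses. Sections 3.1 and 5.6.1 encourage keeping the baseline regimen, with adjustment where clinically needed. The PRN route is open to most patients under their existing prescription, and it is the route that section 11.1.3 leaves out of the variable.

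The companion measure may not make up for this. The NRS asks for average pain over the previous 7 days, and pain relieved by extra PRN doses is scored as relieved. Both measures could then look flat while opioid need rises, and the report would lean towards no reversal of analgesia.

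**Working it through.** There is no figure in the plan to reproduce: section 12.3 states that no formal sample size calculation was done, and section 12.2 that no statistical testing is planned. The check has two parts.

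**1. Following breakthrough opioid through the protocol**

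| Step | Maintenance | Breakthrough |
|---|---|---|
| Recorded from R1, all patients (6.3.6, Table 1) | yes | yes |
| Used for eligibility, new patients (3.1, 4.1) | yes | yes |
| In the safety variable lists (synopsis, 6.3.1) | yes, through mean daily opioid dose | no separate variable |
| In the derivation (11.1.3) | yes | expressly left out |
| In the analyses (12.2.1) | yes, by interval | none specified |

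After randomization, breakthrough data are collected at every visit with no stated analytic use. They are also recorded at Months 4, 5, 7, 8, 10 and 11, when the NRS is not collected (section 3.1.2, Table 1).

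**2. What the restriction hides, for an illustrative patient**

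Inputs:
- Appendix H: 10 mg oral oxycodone counts as 15 mg oral morphine equivalents.
- Section 4.1: permitted maintenance is 30 to 1000 mg/day.
- Assumed, because the documents give no breakthrough frequency or dose size: k doses a day, up from none, each of d mg morphine equivalents, with maintenance M unchanged.

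Formulas:
- Change in the planned variable = M − M = 0.
- Change in total dose = k × d, or 100 × k × d / M per cent.

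With M = 120, k = 2 and d = 15, the addition is 2 × 15 = 30 mg/day. Total dose goes from 120 to 150 mg/day, and 30/120 = +25%. The planned variable shows 0%. Taking d = 7.5 or 30 instead gives 15/120 = +12.5% or 60/120 = +50%.

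The rise in total dose depends strongly on M. For d = 15:

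| Maintenance, mg/day | k = 2 | k = 4 | Planned variable |
|---|---|---|---|
| 30 | +100% | +200% | 0% |
| 90 | +33.3% | +66.7% | 0% |
| 200 | +15% | +30% | 0% |
| 1000 | +3% | +6% | 0% |

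These are single-patient figures. If a fraction f of an arm behaved like the 120 mg/day patient, the arm mean of total dose would rise by 30 × f mg/day. The protocol gives nothing from which to set f.

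**The case against.** The restriction is deliberate and openly stated, and the synopsis wording about prescribed dose fits it. Maintenance dose is a legitimate variable, and a sustained loss of analgesia over 52 weeks could appear in it. Pain is also followed in other ways: NRS change is analysed at Weeks 1 and 2 and Months 1, 2, 3, 6, 9 and 12, the modified Himmelsbach scale is summarized, and inadequate pain control is a reason for discontinuation (section 5.8). The study is descriptive, and no primary conclusion rests on this one variable. All of this stands, and it limits the severity.

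It does not close the gap. Extra PRN use can mask a change in the NRS. The Himmelsbach scale rates withdrawal signs, not analgesia. Section 6.3.4 keeps ordinary day-to-day fluctuations in pain control out of AE reporting unless they are serious.

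A reader might infer four stronger claims that the documents do not support:
- *Breakthrough use will never be analysed.* The SAP is not shown. Section 11.1.3 fixes the content of one variable and does not bar another. What can be said is that the protocol specifies no such analysis, so a SAP that added one would go beyond 11.1.3 and 12.2.1.
- *The variable is practically fixed by design.* Sections 3.1 and 5.6.1 allow maintenance adjustments according to clinical need.
- *Breakthrough use would be the first sign of lost analgesia.* This is plausible given the expected PRN prescribing, but the protocol does not say so.
- *The error is threefold.* Going from 30 to 90 mg/day is correct arithmetic for four 15 mg-equivalent doses at the lowest permitted maintenance dose, but that is one extreme patient.

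**Conclusion.** The point holds at moderate severity. The protocol names daily opioid dose as one of two measures for assessing pain, then defines it so that PRN compensation cannot appear in it, and specifies no other analysis of the breakthrough data it collects. Because PRN doses could also keep the NRS down, the lean is towards no reversal of analgesia. In the illustration, a 25% rise in total dose is shown as 0%. That size rests on the assumed dose, frequency and maintenance level. The direction rests only on some patients using PRN opioid to compensate. No bias at arm level is shown.

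The lack of a stated change from baseline for opioid dose is not part of the finding. The randomized comparison between arms does not need it, and section 12.2 already sets general baseline rules for safety parameters.

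**What to change.** In sections 11.1.3 and 12.2.1, keep mean daily maintenance dose as it is and add two rows by treatment arm:
- total daily opioid dose, meaning maintenance plus breakthrough, in oral morphine equivalents by Appendix H;
- breakthrough dose alone, in the same units.

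Use the existing intervals from randomization in this study: to Month 1, then Months 1 to 3, 3 to 6, 6 to 9 and 9 to 12. Show the number of days with data for each, and say how a day with no breakthrough entry is treated. State in the synopsis and in section 6.3.1 which dose each variable refers to.

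Read the new rows through the randomized comparison between arms, which share the same collection method. Do not compute change from baseline for breakthrough use. Before R1 it is captured only in the eDiary for new patients (section 6.3.6), and for rollover patients the R1 value is a recorded regimen (sections 3.1.2.1 and 6.2.1). After R1 it comes from the home diary and eCRF, so a difference would mix instruments.

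The cost is wording and some programming before database lock, with no new data collection and no change to patient care. The drawback is that home-diary breakthrough data are noisier than maintenance prescriptions, which is why the maintenance row stays and the days of data are shown.

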4. NEW PATIENTS ONLY: Receiving a stable maintenance opioid regimen consisting of a total daily dose of 30 mg to 1000 mg of oral morphine, or equianalgesic amount(s) of 1 or more other opioid therapies (see [Appendix H](#)) for a minimum of 4 weeks prior to screening for non-cancer-related pain with no anticipated change in opioid dose requirement over the proposed study period as a result of disease progression. The opioid regimen should be confirmed by a prescription or medication bottle. Regimen stability will be confirmed during the 2-week OIC confirmation period. Patients will be disqualified from randomization if they consume >4 additional breakthrough pain medication doses per day for more than 3 days during the 2-week OIC confirmation period, or if their long-acting maintenance opioid dose was modified during this same period. The use of additional doses of opioids for breakthrough pain will be captured in the eDiary during the 2-week OIC confirmation period. Patients who are receiving only short-acting opioids will be allowed in the study if they are receiving doses according to a fixed schedule. Patients who are receiving only a short-acting opioid on an as-needed basis that does not follow a fixed schedule, are not eligible for this study. Intrathecal dosing is permitted as long as the patient is taking another orally dosed opioid that meets the dosing and duration criteria defined above.

PATIENTS ENROLLING FROM OTHER NKTR-118 STUDIES: Receiving a stable maintenance opioid regimen consisting of a total daily dose of 30 mg to 1000 mg of oral morphine, or equianalgesic amount(s) of 1 or more other opioid therapies (see [Appendix H](#))

5. NEW PATIENTS: Willingness to stop all laxatives and other bowel regimens including prune juice and herbal products throughout the 2-week OIC confirmation period and the 52-week treatment period, and to use only bisacodyl as rescue medication if a BM has not occurred within at least 72 hours of the last recorded BM.

FOR PATIENTS RANDOMIZED TO RECEIVE NKTR-118: Willingness to stop all laxatives and other bowel regimens including prune juice and herbal products throughout the 52-week treatment period, and to use only bisacodyl as rescue medication if a BM has not occurred within at least 72 hours of the last recorded BM.

FOR PATIENTS RANDOMIZED TO THE USUAL CARE ARM: Willingness to adhere to using approved laxatives throughout the 52-week treatment period.

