- C-SSRS for new patients (obtained from last visit of the previous NKTR-118 study for rollover patients)
- Prior and current medications for new patients. Concomitant medications (other than laxative or opioid medication) ongoing at the end of the previous NKTR-118 study will be recorded for rollover patients.
- Laxative medication use over the past 60 days recorded for new patients. Laxative medication ongoing at the end of the previous NKTR-118 study will be recorded for rollover patients.
- eDiary device training and distribution for NEW Patients only
- Daily maintenance opioid dosing regimen and opioid medication for breakthrough pain over the past 60 days recorded for new patients. Daily maintenance opioid

dosing regimen and opioid medication for breakthrough pain at the start of the present study will be recorded for rollover patients.

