12.2.1 Safety analyses

Adverse events will be coded using the MedDRA dictionary. Three sets of AE summaries will be generated: (1) all AEs recorded in the clinical database, (2) all TEAEs (as defined in Section 11.1.1), and (3) AEs occurring after the last dose of study drug.

Number of events and proportions will be tabulated by preferred term and system organ class. An event that occurred 1 or more times on the date of or subsequent to first dose of study drug will contribute 1 observation to the numerator of the proportion. The denominator of the proportion will comprise all patients in the Safety analysis set. Adverse events will also be

summarized by intensity and separately, by causality (as determined by the investigator). Should a patient experience the same preferred term/system organ class within multiple intensity or causality categories, the patient's worst occurrence (most severe/most related) will be retained in the tabulations. Serious AEs and commonly occurring AEs will be summarized in a generally similar manner. Adverse events of special interest may be further summarized and analysis of AEs occurring within specific time periods (e.g. after 3 months, after 6 months, etc.) may be considered.

Adverse events, SAEs, AEs leading to death, and AEs leading to study discontinuation will be tabulated for each treatment group. Descriptive statistics for time to onset and duration of select AEs may be summarized by treatment group. Adverse events that could potentially be indicative of centrally mediated opioid withdrawal, abuse potential, and bowel perforation will be identified prior to database lock and will also be summarized by each treatment group.

The mean daily opioid dose will be summarized for the following intervals: randomization to Month 1, Months 1 to 3, Months 3 to 6, Months 6 to 9, and Months 9 to 12. The mean bisacodyl dose per week will be summarized only for the NKTR-118 treatment group using descriptive statistics for the following intervals: randomization to Month 1, Months 1 to 3, Months 3 to 6, Months 6 to 9, and Months 9 to 12. The observed composite modified Himmelsbach score and change from baseline will be summarized by treatment group at Week 1, Months 1, 3, 6, 9, and 12 using descriptive statistics. The observed score and change from baseline in the NRS pain scores (average in the 7 days prior to the study visit) will be summarized by treatment group for Weeks 1 and 2, Months 1, 2, 3, 6, 9, and 12.

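### Daily opioid dose is summarized only as post-randomization interval means, with no change from baseline, so a within-patient rise can be obscured if dropout depends on dose

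*Protocol*

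**What the plan says.** The safety variable in section 6.3.1 is "Mean daily opioid dose for Months 1, 3, 6, 9, and 12". The same list gives the pain score as a change: "Change from baseline in NRS pain score for Week 1, Week 2, Months 1, 2, 3, 6, 9, and 12".

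Section 11.1.3 derives the opioid variable from maintenance dosing only; breakthrough doses are recorded but left out. A patient's doses in an interval are summed and "divided by the number of days within the interval in which the data were collected". The intervals are set as follows: "The mean daily opioid dose will be calculated for the following time intervals: randomization in this study to Month 1", then Months 1 to 3, 3 to 6, 6 to 9 and 9 to 12. Rollover patients get extra windows that start at randomization in the previous study.

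Section 12.2.1 plans the matching summary: "The mean daily opioid dose will be summarized for the following intervals: randomization to Month 1, Months 1 to 3, Months 3 to 6", and so on to Month 12. Its paragraph on change from baseline covers laboratory tests, vital signs, ECG, temperature, respiratory rate and weight. Opioid dose is not among them.

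Section 12.2 does define a general baseline. For new patients it is the last value before first dose in this study. For rollovers the primary baseline precedes the pivotal study, and the supportive one is the final visit of the previous study.

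The entry criterion for both new and rollover patients is "Receiving a stable maintenance opioid regimen consisting of a total daily dose of 30 mg to 1000 mg of oral morphine" or its equivalent (section 4.1, criterion 4).

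**The concern.** Change in opioid dose is one of the protocol's own indicators of lost analgesia. Section 3.2 names "the NRS along with ongoing assessment of daily opioid dose to assess pain". Section 1.4 cites the absence of change in daily opioid dose, together with the pain score, as the Phase II evidence that analgesia was not reversed. Because sections 3.1 and 5.6.1 allow opioid adjustment for clinical need, the pain score could stay flat precisely because the dose went up. Dose change would then carry the signal.

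The planned summary does not isolate that change. The first interval is already on treatment, so it is not a baseline. The extra rollover windows also begin at a randomization and pool earlier with current treatment, so they supply no pre-treatment value. Each interval mean comes from whoever still has data. Section 5.8 says discontinued patients are not replaced and lists inadequate pain control as a reason to discontinue, which makes a link between opioid need and dropout plausible, though not established.

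**Working it through.** **Inputs from the protocol.** Eligible entry dose 30 to 1000 mg/day, so the limits differ by 1000/30 = 33-fold. About 1135 patients randomized 2:1, so 1135 × 2/3 = 757 on NKTR-118. The protocol states no figure for this variable that could be reproduced, and no dose distribution, dropout rate or within-patient correlation. Everything below beyond these inputs is assumed.

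**1. Two-group illustration (assumed mix and retention).** 80% of patients on 80 mg/day and 20% on 400 mg/day; 12-month retention 60% and 40% respectively.
- Starting mean: 0.8 × 80 + 0.2 × 400 = 144.
- Mean of those remaining, no dose changed: (0.48 × 80 + 0.08 × 400) / (0.48 + 0.08) = 70.4 / 0.56 = 125.7, a fall of 13%.
- Every dose up 10%: 125.7 × 1.10 = 138.3, still 4% below 144.
- Within-patient change among those remaining: +10%.

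**2. Comparison with Usual Care in the same illustration.**
- Same retention in both arms: Usual Care 125.7, NKTR-118 138.3; ratio 1.10. The rise shows in full.
- Usual Care dropout unrelated to dose: Usual Care stays at 144, NKTR-118 is 138.3; ratio 0.96. The rise is hidden.

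**3. How few high-dose losses are enough.** Let n patients have mean M, let k patients at 1000 mg/day leave, and let everyone else rise by a factor r. The observed mean is unchanged when k = nM(r − 1) / (1000r − M). With n = 757:

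| Assumed M (mg/day) | k hiding a 10% rise | k hiding a 20% rise |
|---|---|---|
| 100 | 8 | 14 |
| 140 | 11 | 20 |
| 180 | 15 | 27 |

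At M = 140 and r = 1.1: 757 × 140 × 0.1 / (1100 − 140) = 11.0, or 1.5% of the arm. This is an extreme case, because every patient lost is at the eligibility ceiling.

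**4. Smoother dropout model (assumed).** Entry doses log-normal, truncated to 30–1000 mg/day, median 60 to 120, log-SD 0.6 to 1.0; dropout odds multiplied by a fixed ratio for each doubling of dose. The table gives the uniform rise that leaves the observed mean unchanged.

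| Retention | Odds ratio 1.0 | Odds ratio 1.5 |
|---|---|---|
| 80% | 0% | 3.5–9% |
| 40% | 0% | 10–27% |

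For median 90 and log-SD 0.8 the starting mean is 132. With 40% retention and odds ratio 1.5, a true 20% rise leaves an observed mean of 132.

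**5. Precision.** With equal variances at both times and within-patient correlation ρ, the standard error of a between-arm difference in level, divided by that of a difference in change, is 1/√(2(1 − ρ)). This exceeds 1 when ρ > 0.5. It is 1.58 at ρ = 0.8 and 2.24 at ρ = 0.9 (both assumed). This point does not need dose-related dropout.

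**6. Is a baseline recoverable?** Yes. Section 6.3.6 records the maintenance dose at all visits, and Visit R1 records it among the pre-dose assessments (section 3.1.2.1). Section 6.2.1 adds "Daily maintenance opioid dosing regimen and opioid medication for breakthrough pain over the past 60 days recorded for new patients", and the dose at study start for rollovers. The extra rollover windows in 11.1.3 already require opioid data from the previous study.

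**The case against.** The strongest reply is that a baseline does exist. Section 12.2 defines one without limiting it by variable, opioid dose is a listed safety variable, and change from baseline for rollovers is promised where appropriate. A SAP is to follow, and nothing in the protocol forbids adding the change there. This stands in part: it would be wrong to infer that no baseline can be derived. What remains is that the protocol specifies both derivation and summary for this variable and, unlike its neighbours, gives it no change.

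Second, there is a randomized comparator. This stands: step 2 shows that dose-related dropout equal in both arms leaves the relative comparison intact.

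Third, a reader might infer that the interval means will mainly reflect who stays, or that doses really vary 33-fold. The documents support neither. The 33-fold figure is a ratio of eligibility limits, and no link between dose and dropout is documented. Nor is the target of about 125 patients with 12 months of NKTR-118, 16.5% of 757, a retention forecast; it is an exposure count.

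Fourth, no testing is planned, so precision matters less. That is fair, but descriptive differences are still read against their spread.

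Fifth, other measures bear on analgesia and withdrawal: change in pain score, the modified Himmelsbach scale, withdrawal-type adverse events, and an outlier analysis of major safety variables. These reduce the stakes. They do not replace dose change when the dose is what was adjusted, and section 12.2 does not name opioid dose in the outlier analysis.

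**Conclusion.** The point holds as a weakness in how one safety variable is summarized, and the protocol itself uses that variable as evidence on analgesia. Post-randomization interval means can obscure a within-patient rise over time if dropout is related to dose, and between arms only if that dropout also differs by arm. Under the assumptions shown, the rise that could be hidden runs from nothing (dropout unrelated to dose) through 3.5–9% (80% retention, odds ratio 1.5 per doubling) to 10–27% (40% retention, same odds ratio). None of these is a prediction for this trial. The loss of precision is separate and needs only a within-patient correlation above 0.5. This does not show that a signal will be missed, and no data are lost. It is an improvement available at almost no cost.

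**What to change.** In 11.1.3 and 12.2.1, apply the section 12.2 baseline to maintenance opioid dose:
- **New patients:** the latest regimen recorded before first dose (R1).
- **Rollovers:** the dose before the pivotal study as primary baseline, and the dose at the final visit of the previous study (R1) as supportive baseline. R1 alone would not do, because for a patient already given NKTR-118 it is an on-treatment value and would hide an earlier rise.

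For each interval, summarize within-patient change and percent change by arm, and by new or rollover status, beside the observed means and with the number of patients contributing. State that this removes the shifting mix of entry doses but not the bias that arises if patients leave because their dose or pain rose.

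The cost is a few sentences and one added table, with no new data collection in this study. The pre-pivotal dose has to come from the earlier study databases, from which section 12.2 already plans to pull baseline data.
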